4.3.2.3.5 Baseline Adjusted AUC_{0-t}

The baseline adjusted AUC_{0-t} is calculated as

$$BaseAdjAUC_{0-t} = AUC_{0-t} - GIR_0 * t$$

4.3.2.3.6 Baseline Adjusted $AUC_{0-\infty}$

The baseline adjusted $AUC_{0-\infty}$ is calculated as

$$BaseAdjAUC_{0-\infty} = (AUC_{0-last} - GIR_0 * t_{last}) + (GIR_{last} - GIR_0/\lambda)$$

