4.3.2.3.1 GIR_{max}

GIR_{max} will be the maximum GIR readings from time 0 to time 300 minutes.

- In a “No Peak” case, this will be set as missing.

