4.3.2.3.2 Terminal Rate Constant λ

Terminal rate constant λ is needed before we estimate AUC_{0-t} . It is estimated by:

- a. Find the GIRs after GIR_{max} (section 4.3.2.3.1)
 - i. If there only 1 or 0 available GIR reading after GIR_{max} , then λ will be set as missing.
- b. Do a regression of log-transformed GIR vs Time
- c. λ is the slope from this regression
- d. In a “No Peak” case, λ will be set as missing

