4.3.2.3.3 AUC_{0-t}

The AUC_{0-t} of GIR over wear time will be calculated using trapezoid rule and the actual time points. Missing data for the calculation of the AUC will be handled as followed:

1. If the reading for Time 0 is missing, it will be the average of up to 3 prior readings. However, if there is no prior readings available, it will be assumed to be 0
2. If the reading at (actual) time t ($t < 300$ min) is missing, it will be imputed with linear interpolation
3. If the reading at $t=300$ min is missing:
 - a. The reading at $t=300$ min will be imputed using the regression line obtained when estimate λ (section 4.3.2.3.1).
 - b. If λ is missing, AUC_{0-t} will be set as missing.

4.3.2.3.4 $AUC_{0-\infty}$

$AUC_{0-\infty}$ is estimated as

$$AUC_{0-\infty} = AUC_{0-last} + AUC_{last}, \text{ where } AUC_{last} = GIR_{last}/\lambda$$

If λ is missing, then $AUC_{0-\infty}$ is set as missing.

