4.4.4.2.3 PD Parameters

All PD parameters will be presented descriptively.

Additionally, AUCs, t_{50} , GIR_{max} , $t_{max(GIR)}$, and Duration of Insulin Action will be tested for treatment effects. The effects between Achilles and control set will be compared in a mixed-effects (repeated-measures) linear model with *treatment* and *period* as fixed effects and *participant* as a random effect. Log-transformation will be applied if data distribution is found to be highly skewed.

The mean difference between treatments (or on the log-scale) will be compared with a two-sided test using significance level $\alpha=0.05$. Then mean ratio and its 95% confidence interval will be calculated

- Inverse-transforming will be done if the variable was log-transformed.

Secondary analyses will use the both ITT and PP populations for analysis. Multiple comparisons may raise these tests. We are not considering any correction in this SAP.

Population	ITT and PP (ITT is the primary , PP is the sensitivity)
------------	---

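### The baseline-adjusted AUC0–∞ formula divides only the baseline GIR by λ, so it adds a rate to an area and drops nearly all of the extrapolated tail

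*SAP*

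**What the plan says.** SAP 4.3.2.3.6 builds the baseline-adjusted AUC0–∞ from two brackets: "AUC_{0-last} - GIR_0 * t_{last}) + (GIR_{last} - GIR_0", then a slash, λ and the closing bracket. The first bracket is the observed area less the baseline area. The second is meant to be the extrapolated tail, and in it λ divides GIR0 alone.

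The neighbouring definitions are:

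- **Unadjusted AUC0–∞ (SAP 4.3.2.3.4):** the total is "AUC_{0-last} + AUC_{last", and the tail is "AUC_{last} = GIR_{last" divided by λ.
- **Baseline-adjusted AUC0–t (SAP 4.3.2.3.5):** "BaseAdjAUC_{0-t} = AUC_{0-t} - GIR_0 * t".
- **λ (SAP 4.3.2.3.2):** the instruction is "Do a regression of log-transformed GIR vs Time", using the readings after the maximum, and λ "is the slope from this regression".
- **Time scale (SAP 4.3.2.3.1):** minutes; GIRmax "will be the maximum GIR readings from time 0 to time 300 minutes".

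On use, SAP 4.4.4.2.3 states "All PD parameters will be presented descriptively" and also lists AUCs, not itemised, among the parameters tested for a treatment effect.

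**The concern.** A baseline adjustment should change nothing when the baseline is zero, and every term in an AUC should be an area. The printed formula fails both conditions. A programmer who codes it literally would produce a baseline-adjusted AUC0–∞ that contradicts the unadjusted one beside it, even in participants with no baseline infusion to adjust for.

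The shortfall depends on GIRlast and λ, and is largest where glucose-lowering action is still present at 300 minutes. It would therefore vary between clamps and need not cancel between devices or wear days. This is a separate fault from the sign of λ, and correcting the sign does not repair the bracket.

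**Working it through.** The plan states no numerical result for this parameter, so there is no figure to reproduce. The check is of units, algebra and size.

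**Inputs from the documents**

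- GIR is in mg/kg/min; the clamp's dextrose range is 0.1 to 4 mg/kg/min (Protocol 6.1.1.5).
- Time is in minutes, so λ, a slope of log GIR on time, is per minute.
- GIR0 should normally be 0. IV infusions stop 20 minutes before the bolus, and dextrose starts only once glucose is 5 mg/dL below the Baseline Part II mean (Protocol 6.1.1.5).

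**Assumed inputs (not in the documents)**

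- λ of 0.005 to 0.02 per minute, taken as positive; GIRlast of 0.5 mg/kg/min; GIR0 of 0 or 0.1 mg/kg/min.

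**Step 1: units.** AUC0–last, GIR0 × tlast and GIR0/λ are all in mg/kg. GIRlast alone is in mg/kg/min. The sum therefore depends on the time unit. Take λ = 0.01 per minute, GIRlast = 1 mg/kg/min and GIR0 = 0:

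- In minutes, the printed tail is 1 and the consistent tail is 1/0.01 = 100 mg/kg.
- In hours (GIR = 60 mg/kg/h, λ = 0.6 per hour), the printed tail is 60 and the consistent tail is 60/0.6 = 100 mg/kg.

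A true area does not change with the unit; the printed one does.

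**Step 2: reduction to the unadjusted form.** Set GIR0 = 0. The adjusted AUC0–t of 4.3.2.3.5 becomes AUC0–t, as it should. The adjusted AUC0–∞ of 4.3.2.3.6 becomes AUC0–last + GIRlast, whereas 4.3.2.3.4 gives AUC0–last + GIRlast/λ.

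**Step 3: algebra.**

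- Printed tail = GIRlast − GIR0/λ
- Consistent tail = (GIRlast − GIR0)/λ
- Consistent − printed = GIRlast/λ − GIRlast = (GIRlast/λ)(1 − λ)

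GIR0 cancels, so the error is present for every clamp with a non-zero last reading, whatever the baseline. With λ in per-minute units, the shortfall is the fraction (1 − λ) of GIRlast/λ.

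**Step 4: size of the tail error (GIRlast = 0.5, positive λ).**

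| λ (per min) | GIR0 | Consistent tail (mg/kg) | Printed tail |
|---|---|---|---|
| 0.005 | 0 | 0.5/0.005 = 100 | 0.5 |
| 0.01 | 0 | 0.5/0.01 = 50 | 0.5 |
| 0.02 | 0 | 0.5/0.02 = 25 | 0.5 |
| 0.005 | 0.1 | 0.4/0.005 = 80 | 0.5 − 20 = −19.5 |
| 0.01 | 0.1 | 0.4/0.01 = 40 | 0.5 − 10 = −9.5 |
| 0.02 | 0.1 | 0.4/0.02 = 20 | 0.5 − 5 = −4.5 |

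With GIR0 = 0 the loss is 99.5%, 99% and 98% of the tail. The printed tail turns negative once GIR0 exceeds λ × GIRlast, which is only 0.005 mg/kg/min at λ = 0.01.

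**Step 5: effect on the whole parameter.** As an illustration, take an assumed curve GIR(t) = 4(t/tp)exp(1 − t/tp), which peaks at 4 mg/kg/min at time tp, with GIR0 = 0, the protocol's glucose sampling times, and λ fitted to the readings after the peak.

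- tp = 90 min: λ = 0.0058, GIRlast = 1.29, AUC0–300 = 826.8. Consistent total 826.8 + 223.0 = 1049.8; printed total 828.1. Shortfall 221.7/1049.8 = 21%.
- tp = 120 min: λ = 0.0035, GIRlast = 2.23, AUC0–300 = 929.5. Consistent total 929.5 + 636.2 = 1565.7; printed total 931.7. Shortfall 634.0/1565.7 = 40%.

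In both cases the consistent total equals the unadjusted AUC0–∞, as it must when GIR0 = 0.

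**Step 6: sign of λ.** Section 4.3.2.3.2 takes the raw slope, which is negative on a falling curve. With that sign and GIR0 = 0, the printed tail is still just GIRlast, so the bracket error remains. With GIR0 = 0.1 and GIRlast = 0.5, the printed tail becomes 0.5 + 0.1/|λ|, that is 20.5 to 5.5 for |λ| of 0.005 to 0.02. The negative entries in the table therefore rest on the assumed positive λ.

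**The case against.** The strongest reply is that this is a misplaced bracket whose intended form is clear from the two preceding subsections, and that it touches almost nothing.

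- **Possible text-conversion fault.** The formula was read from PDF, and one bracket decides the matter. This cannot be excluded without the source page. However, the printed expression is complete, its brackets balance, and the neighbouring formulas came through intact.
- **A programmer may code the intended form anyway.** True, and the documents do not show what was coded. But the SAP is the specification, and nothing elsewhere in it corrects the formula.
- **Reach is small.** This stands. The primary variable is AUC0–300; its baseline-adjusted repeat in SAP 4.4.4.1 is also AUC0–300; and the percentage parameter in SAP 4.3.2.4.5 uses AUC0–300 as denominator. The protocol's pharmacodynamic endpoints mention AUC0–∞ only as a denominator, and never baseline-adjusted. Because the tested AUCs are not itemised, a formal test of this parameter is an inference; its descriptive presentation is not.
- **No tail, no error.** This also stands: where GIR has returned to 0 by the last reading and GIR0 is 0, both forms give zero.
- **A share of the tail overstates the effect on the parameter.** Fair. The effect on the total depends on how much action remains at 300 minutes; the two illustrative curves give 21% and 40%, with higher last readings than the 0.5 used for the tail table.
- **The trial stopped after the 7th completer** (SAP 2.5), so some outputs may never appear. That lowers the practical stakes but does not make the definition right.

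**Conclusion.** The formula is wrong as printed. It mixes a rate with areas and, at GIR0 = 0, disagrees with the SAP's own unadjusted AUC0–∞. Those two conclusions follow from the SAP's definitions and the protocol's GIR unit, and need no assumed values.

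The size does rest on assumptions: minutes as the time unit, a positive λ of 0.005 to 0.02 per minute, and GIRlast of 0.5 mg/kg/min. On those, 98% to 99.5% of the tail is lost when GIR0 is 0, and the tail is negative when GIR0 is 0.1. The consequence is confined to one secondary pharmacodynamic parameter. The primary analysis and the sample size do not depend on it, so this is a minor correction.

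**What to change.** Check the bracket against the source page. If it is as printed, do one of the following:

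1. Replace the tail in SAP 4.3.2.3.6 with (GIRlast − GIR0)/λ, and define λ in 4.3.2.3.2 as minus the regression slope, so that it is a positive decay constant here and in 4.3.2.3.4. Moving the bracket without settling the sign would give a negative tail whenever GIRlast exceeds GIR0.
2. Delete the parameter. It is not a protocol endpoint and, when GIR0 is 0, it only repeats the unadjusted AUC0–∞.

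If it is kept, note that the corrected form is approximate when GIR0 is above 0, because λ is fitted to unadjusted GIR. On the illustrative curve with tp = 90 min, adding a constant GIR0 of 0.1 gives 1059.4 against 1049.8, about 1% high.

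The cost is one formula in the SAP, the matching line of the program, and a check of any output already produced. A useful program test is that adjusted and unadjusted AUC0–∞ agree exactly whenever GIR0 is 0.

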4.3.2.4 Other GIR Parameters

4.3.2.4.1 Time-to-Maximum GIR ($t_{max(GIR)}$)

$t_{max(GIR)}$ is the minute between the time corresponding to GIR_{max} and Time 0. Actual time will be used in this calculation.

- If GIR_{max} is missing, $t_{max(GIR)}$ will also be set as missing.
- If the same Maximum value appears at two or more time point, the Time to Maximum will be estimated based on the first occurrence of maximum value.

4.3.2.4.2 Time to Half-Maximal GIR, Both Early and Late ($t_{50(GIR),early}$ & $t_{50(GIR),late}$)

$t_{50(GIR),early}$ is the time in minutes from 0 min to the time when GIR rises to half way to the maximum. It is calculated as followed:

- $t_{50(GIR),early} = \text{Time corresponding to } \frac{(GIR_{max} - GIR_0)}{2} - t_0.$
- If GIR_{max} is missing, $t_{50(GIR),early}$ will also be set as missing.

$t_{50(GIR),late}$ is the, It is estimated as:

- $t_{50(GIR),late} = \text{Time corresponding to } \frac{(GIR_{max} - GIR_{300})}{2} - t_0.$
- If GIR_{300} is missing, it will be imputed as described in section 4.3.2.2.3.

All calculation will be based on the actual time.

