Secondary Endpoints 1:	
Mean differences (within treatments over time and between treatments at specified time points) in:
 
 Time-to-Maximum Glucose Infusion Rate (GIR) ($t_{max(GIR)}$) Time to half-maximal GIR, both early and late ($t_{50(GIR),early}$ & $t_{50(GIR),late}$) Onset of action as measured by a drop of blood glucose (BG) by 5 mg/dL Duration of insulin action (calculated the same as MRT for PK) GIR_{max} Area under the GIR curve ($AUC_{0-t(GIR)}$), both absolute and as a percentage of total $AUC_{0-\infty}$ and Coefficient of Variation (CV) of $AUC_{0-t(GIR)}$, where $t = 5, 10, 15, 20, 30, 45, 60, 90, 120, 150, 180, 210, 240,$ and 300 min 
Other PD parameters may also be calculated.

Secondary Objective 2:	To assess pharmacokinetic (PK) parameters within and across treatments following subcutaneous delivery using Achilles vs Teflon control set on DOI and days 3, 5, and 7 post insertion.
Secondary Endpoints 2:	
Mean differences (within treatments over time and between treatments at specified time points) in:
 
 • Early exposure ($AUC_{0-60min}$) • Mean-residence time (MRT) of insulin • Maximum Insulin concentration (C_{max}) • Time-to-Maximum Insulin Concentration (t_{max}) • Time-to-50% Maximum Insulin Concentration [$t_{50,early}$ & $t_{50,late}$], both early (i.e. before C_{max}) and late (i.e. after C_{max}) • $AUC_{(0-t)}$ (both absolute and as a percentage of $AUC_{(0-300)}$) and Coefficient of Variability (CV) $AUC_{(0-t)}$ where $t = 3, 6, 9, 12, 15, 20, 25, 30, 35, 40, 45, 50, 60, 70, 80, 90, 105, 120, 150, 180, 210, 240$ and 300 min 
Other PK parameters may also be calculated.

Secondary Objective 3:	To assess continuous glucose monitoring (CGM) data, comparing data within and across treatments.
Secondary Endpoints 3:	
 • Mean daily time in range (70-180 mg/dL), DOI through Day 7 inclusive • Mean daily time in target (70-140 mg/dL), DOI through Day 7 inclusive • Mean and median daily glucose, DOI through Day 7 inclusive • Glucose variability (%CV), DOI through Day 7 inclusive • Mean daily time ≤ 70 mg/dL, < 54 mg/dL, DOI through Day 7 inclusive • Mean daily time > 140 mg/dL, > 180 mg/dL, > 240 mg/dL, DOI through Day 7 inclusive • Other CGM metrics may also be calculated
Secondary Objective 4:	To assess performance of investigational infusion set on DOI through 7 for each treatment

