4.3.2.4.3 Onset of Insulin Action

The onset of insulin action is defined as the time in minutes from the beginning of baseline to the first occurrence of a drop in blood glucose concentration by 5 mg/dL from its maximum. It will be based on the actual time.

- If the blood glucose never dropped by 5 mg/dL from time 0, it will be set as missing.

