4.3.2.5.8 Time-to-50% Maximum Insulin Concentration [$t_{50,early}$ & $t_{50,late}$]

$t_{50,early}$ & $t_{50,late}$ will be calculated with the same methods as described in section 4.3.2.4.2.

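### SAP formulas for t50 (early and late), GIR AUC0-infinity and onset of action do not compute the quantities they name

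*SAP*

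**What the plan says.** **t50.** The protocol synopsis lists time to half-maximal GIR, early and late, and for insulin "Time-to-50% Maximum Insulin Concentration", early and late. SAP 4.3.2.4.2 describes early t50 in words: it "is the time in minutes from 0 min to the time when GIR rises to half way to the maximum". Its formula then looks up the level (GIRmax - GIR0)/2. The sentence that should define late t50 is unfinished, and only the formula remains, with numerator and divisor "GIR_{max} - GIR_{300})}{2} - t_0". For insulin, SAP 4.3.2.5.8 says both times "will be calculated with the same methods as described in section 4.3.2.4.2". SAP 4.4.4.2.2 and 4.4.4.2.3 test t50 between sets for PK and PD.

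**AUC0-infinity.** SAP 4.3.2.3.2 regresses log GIR on time after the peak and says lambda "is the slope from this regression". SAP 4.3.2.3.4 adds a tail, "AUC_{last} = GIR_{last" over lambda, to AUC0-last. The baseline-adjusted version in SAP 4.3.2.3.6 reads, in the extracted text, "AUC_{0-last} - GIR_0 * t_{last}) + (GIR_{last} - GIR_0" with only the final GIR0 divided by lambda.

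**Onset.** SAP 4.3.2.4.3 defines onset as "the time in minutes from the beginning of baseline to the first occurrence of a drop in blood glucose concentration by 5 mg/dL" from the glucose maximum. Its missing-value rule refers instead to a 5 mg/dL drop from time 0. Protocol 6.1.1.5 defines baseline glucose as the mean of the values from -20 to 0 min. It also sets the dextrose trigger at 5 mg/dL below the Baseline Part II mean (-15, -10 and -5 min).

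**The concern.** Half the difference between the maximum and another point is not half the maximum. Nor is it the midpoint between the two values, which would need a plus sign. The t50 error depends on each profile's own time-0 or 300-min value, so it is not a constant that cancels in the crossover. Followed literally, the SAP would put shifted or undefined t50 values into formal PK and PD tests.

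A negative lambda gives an area to infinity smaller than the area already observed. Taken as a percentage of that total, which the protocol lists as an endpoint, the GIR AUC would exceed 100% at late times.

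An onset clock that starts before the bolus, with the drop taken from a maximum, can register an onset before any bolus insulin is given.

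**Working it through.** **Inputs.** The formulas are those above. GIR at time 0 is normally 0, because Protocol 6.1.1.5 stops the IV infusions 20 min before the bolus. Insulin at time 0 is expected to be above 0: the pump runs at 0.1 U/h throughout, and IV insulin stops only 20 min earlier. GIR at 300 min can be above 0, because the clamp ends at 5 hours whether or not GIR has returned to 0. Neither document gives insulin or GIR levels, so the curves below are assumptions.

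**t50 algebra.** Let M be the maximum, y0 the time-0 value and y300 the 300-min value.

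- Early: M/2 - (M - y0)/2 = y0/2, so the SAP level is too low by y0/2. Against the midpoint (M + y0)/2 it is too low by y0.
- Late: M/2 - (M - y300)/2 = y300/2, so the SAP level is again too low and late t50 comes out too late.
- On a steadily falling limb the late level is reached only if (M - y300)/2 >= y300, that is, y300 <= M/3. For y300 between M/3 and M/2 the curve does fall to 50% of maximum, but the SAP level is never reached.

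**Insulin.** Assumed y = C0 + (60 - C0)(t/60)exp(1 - t/60), with peak 60 at 60 min. Times are in minutes.

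| C0, % of Cmax | C300 | early, SAP | early, 50% of max | late, SAP | late, 50% of max |
|---|---|---|---|---|---|
| 5 | 8.2 | 12.1 | 13.0 | 181.0 | 165.8 |
| 10 | 10.9 | 10.2 | 12.0 | 194.9 | 171.8 |
| 20 | 16.4 | 6.1 | 9.7 | 238.0 | 187.1 |
| 25 | 19.1 | 3.9 | 8.5 | 279.0 | 197.4 |
| 30 | 21.8 | 1.6 | 7.1 | none | 210.5 |

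In the last row C300 is 21.8/60 = 36% of Cmax, above one third.

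**GIR.** Assumed y = 4(t/tp)exp(1 - t/tp), with GIR0 = 0. Early t50 is then the same under both definitions.

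| tp, min | GIR300/max | late, SAP | late, 50% of max |
|---|---|---|---|
| 80 | 0.24 | 247.8 | 214.3 |
| 90 | 0.32 | 294.1 | 241.1 |
| 100 | 0.41 | none | 267.8 |
| 110 | 0.48 | none | 294.6 |

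**AUC0-infinity.** Take GIR = 4exp(-0.01(t - 100)) from 100 to 300 min. The fitted slope is -0.0100, GIRlast = 4exp(-2) = 0.541, and GIRlast/lambda = -54.1. With an assumed AUC0-last of 600, the SAP gives 600 - 54.1 = 545.9; the correct total is 600 + 54.1 = 654.1. The shortfall is always 2 x GIRlast/|lambda|, here 108.2. At 300 min the percentage of the total would be 600/545.9 = 110% instead of 600/654.1 = 92%.

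A second assumed shape, a linear rise to 8 at 100 min followed by exponential decay, shows the same pattern:

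| decay per min | AUC0-300 | SAP AUC0-infinity | correct |
|---|---|---|---|
| 0.005 | 1412.9 | 825.7 | 2000.0 |
| 0.01 | 1092.3 | 984.5 | 1200.0 |
| 0.02 | 792.7 | 785.5 | 800.0 |

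**Baseline-adjusted tail.** With GIR0 = 0 the bracket as it reads reduces to GIRlast = 0.54, a rate added to an area. The intended tail would be (0.541 - 0)/0.01 = 54.1.

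**Onset.** Starting the clock at baseline adds 15 min (Baseline Part II), 20 min (the -20 min sample) or up to 60 min (Baseline Part I at -60). The permitted stabilization band, 95 ± 15 mg/dL, is 30 mg/dL wide, six times the 5 mg/dL criterion. A qualifying fall before the bolus is therefore possible within range.

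**Primary endpoint.** AUC0-300 uses lambda's regression only to fill in a missing 300-min value. That value is read off the fitted line itself, so the sign causes no error.

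**The case against.** The algebra is not in dispute; the size and weight of the error are.

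- **Insulin baseline.** The assumed insulin curve holds its baseline for 300 min. If the pump's 0.1 U/h were the only sustained source, linear kinetics on the same curve with the 10.5 U bolus of a 70 kg participant put the baseline near 2.5% of Cmax. Early t50 is then 13.0 against 13.5 min and late t50 175 against 163 min, with nothing missing. A sustained 20% would need about 0.97 U/h. This rightly moves attention to the low end of the table. It does not exclude the rest: Protocol 4.3 allows IV insulin at 0.1 to 3.0 U/h, and Protocol 6.1.1.5 foresees insulin infusion during the clamp.
- **GIR range.** With a GIR peak at 50 or 60 min (GIR300 4% or 9% of maximum) the late error is only 3 or 9 min, and it is 0 when GIR returns to 0. That is correct, and the tabulated cases say nothing about how often a high 300-min value will occur. The no-solution result also needs a steadily falling curve, and the SAP has no rule for a level never reached.
- **Treatment contrast.** Bolus per kg, pump rate and dosing weight are the same in both periods, so part of the error is shared between sets. No bias in the contrast has been quantified.
- **Early termination.** The study stopped after the 7th participant completed, and the secondary tests carry no multiplicity correction, so their inferential weight is small. SAP 2.5 nevertheless says all defined analyses will be done.
- **Baseline-adjusted bracket.** It could be a stacked fraction flattened when the PDF was read. That item needs checking against the source; the other items do not depend on it.
- **Lambda.** A programmer might silently use |lambda|. The SAP should not rely on that, and it would not repair t50 or onset.

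**Conclusion.** The concern holds. As written, early and late t50 equal 50% of maximum only when the subtracted value is 0, AUC0-infinity falls below AUC0-last whenever GIRlast is above 0, and onset has a pre-bolus start and two conflicting references.

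The algebraic errors (y0/2, y300/2 and 2 x GIRlast/|lambda|) need no curve, beyond a falling post-peak fit for the last. The sizes in minutes rest on assumed profiles. For late t50 they run from a few minutes, or none, when the 300-min value is near 0, to more than 80 min or no solution when it is near or above one third of the maximum.

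GIR early t50 is normally right. Onset is summarized only descriptively, and part of its error is common to both sets. The damage is confined to secondary parameters, of which t50 is formally tested. This should be corrected, but it does not threaten the primary analysis.

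**What to change.** Amend the SAP as follows.

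- **t50 (4.3.2.4.2, and through it 4.3.2.5.8):** minutes from t0 to the crossing of 50% of the maximum, before the peak for early and after it for late. Set late t50 to missing only if the curve is still above 50% of maximum at 300 min. Point the GIR300 imputation to 4.3.2.3.3; the cited 4.3.2.2.3 does not exist.
- **Lambda (4.3.2.3.2):** minus the regression slope, fitted to positive post-peak values, since the log of a zero GIR is undefined.
- **Baseline-adjusted tail (4.3.2.3.6):** (GIRlast - GIR0)/lambda, after checking the bracket in the source file.
- **Onset (4.3.2.4.3):** minutes from t0 to the first glucose value at least 5 mg/dL below one stated baseline mean, with the same reference in the missing rule. The -20 to 0 min mean or the Baseline Part II mean, both in Protocol 6.1.1.5, would serve; name one.

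The cost is a few lines of SAP text and code. No new data are needed and the primary analysis is unchanged.
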